7.2.1 Study Design

The overall study design proposed, including the dose, regimen, number of healthy control subjects, endpoints, and analyses follows the recommendations from the latest guidelines by FDA and EMA on evaluation of PK in subjects with hepatic impairment (FDA, 2003; EMA, 2005).

The proposed study design includes the enrollment of patients with mild and moderate liver impairment (Child-Pugh class A and B respectively). Subjects with severe hepatic impairment (Child-Pugh class C) will be excluded from the study as outlined above.

The regulatory guidelines include a provision for use of a reduced, sequential study design, to evaluate the group of subjects with higher severity of liver impairment first (such as moderate liver impairment), and if no effect on PK is demonstrated, then these results could be extrapolated to the subjects with liver impairment of lesser severity. In the case of lemborexant, the reduced study design is considered to be unsuitable since a large effect in the moderate hepatic impaired subjects is expected based on the current disposition profile for lemborexant. This design would require subsequent investigation in mild hepatic impaired subjects to ensure clarity regarding lemborexant labeling.

The proposed study design includes 8 subjects per cohort of mild and moderate hepatic impairment and 8 matched control subjects, and will utilize an estimation-based approach to calculate the ratios of the geometric means rather than powering the study to test for a

specific difference in exposure between subjects with hepatic impairment and healthy controls. In addition, 90% CIs for the slope parameter of the relationship between Child-Pugh score and apparent clearance of lemborexant may provide additional indication of any effect (or lack of) on lemborexant PK. This analysis will take into account all subjects' data (N=24), thereby increasing the possibility to detect a relationship between severity of liver impairment and lemborexant PK.

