7.2.2 Assessment of Severity of Liver Impairment

As proposed for the study, both guidelines (FDA, 2003; EMA, 2005) recommend use of Child-Pugh Classification Score as a marker of degree of liver impairment. The EU guidelines also recommend obtaining the adequate range of decreases in serum albumin and increases in bilirubin and prothrombin times. Unlike serum creatinine or creatinine clearance, which have been used to assess the degree of renal impairment, there is no single measure or group of measures that has gained widespread clinical use to estimate the degree of liver impairment. As the Child-Pugh classification system is based on laboratory-based parameters (serum albumin, bilirubin and prothrombin time) and also 2 clinical features (encephalopathy and ascites), the total score relies on the subjective assessments of these features, and hence is associated with variability in estimation of the degree of impairment. Among other models that have been increasingly used as a measure of liver impairment, the model of end stage liver disease (MELD) score, relies only on the laboratory parameters, and thus, is more likely to be consistent between different clinical centers for grading a particular patient for degree of liver impairment. In addition, published reports have indicated a good correlation between the MELD scores and Child-Pugh Scores (Albarmawi et al 2013). Therefore, as per the regulatory guidelines, although the proposed study will use the Child-Pugh Classification as a primary approach for characterizing degree of liver impairment, an exploratory assessment of the correlation between the lemborexant PK and the MELD score will be included to aid clinical guidance. Nonetheless, in agreement with the guidelines, the overall conclusions and dosing recommendations will be based on analysis using the Child-Pugh Scores and their relationship with lemborexant PK.

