8.2 Secondary Objectives

The secondary objectives are:

- To evaluate the effects of hepatic impairment on the PK of lemborexant metabolites M4, M9, and M10.
- To evaluate the relationship between the PK parameters of lemborexant and its metabolites and the Child-Pugh Classification score, serum albumin, total bilirubin, and prothrombin time.

• To assess safety and tolerability of lemborexant following a single dose administration in subjects with mild and moderate hepatic impairment and healthy subjects.

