9.3.1 Inclusion Criteria

Inclusion Criteria for All Subjects

Subjects who meet all of the following inclusion criteria will be eligible for participation in the study.

- 1. Male or female subjects, ages 18 to 79, inclusive, at the time of informed consent.
- 2. BMI between 18 and 40 kg/m², inclusive, at Screening.
- 3. Voluntary agreement to provide written informed consent, and the willingness and ability to comply with all aspects of the protocol.
- 4. Nonsmokers or smokers who smoke 20 cigarettes or less per day.
- 5. For Cohorts A and B: stable (without any change in disease status for at least 60 days prior to study screening) hepatic impairment conforming to Child-Pugh classification A or B, respectively (see Table 1 and Table 2), and documented by medical history and a physical examination.
- 6. For Cohort C: healthy subjects matched to subjects with hepatic impairment with regard to age (± 10 years), sex, and BMI ($\pm 20\%$), and as determined by no clinically significant deviation from normal in medical history, physical examination, electrocardiogram (ECG), and clinical laboratory determinations.

Table 1 Criteria for Child-Pugh Classification							
	Points Scored for Observed Findings						
Clinical or Biochemical Assessments	1 2 3						
Albumin (g/dL)	>3.5	2.8 - 3.5	<2.8				
Bilirubin (mg/dL)	<2	2-3	>3				
PT (seconds prolonged)	<4	4 - 6	>6				
or INR	<1.7	1.7 – 2.3	>2.3				
Ascites	None	Mild/Moderate (diuretic-responsive)	Tense (diuretic-refractory)				
Encephalopathy ^a	None	1 or 2 (or precipitant-induced)	3 or 4 (chronic)				

cps=cycle per second; INR=international normalized ratio; PT=prothrombin time

a: Grade 0: normal consciousness, personality, neurological examination, and electroencephalogram; Grade 1: restless, sleep disturbed, irritable/agitated, tremor, impaired handwriting, and 5 cps waves; Grade 2: lethargic, time-disoriented, inappropriate, asterixis, ataxia, slow triphasic waves; Grade 3: somnolent, stuporous, place-disoriented, hyperactive reflexes, rigidity, slower waves; Grade 4: unrousable coma, no personality/behavior, decerebrate, slow 2-3 cps delta activity.

Table 2 Child-Pugh Classification Scoring				
Total Points Child-Pugh Class				
5 - 6	А			
7 – 9	В			

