9.4.3 Method of Assigning Subjects to Treatment Groups

Subjects will be assigned to 1 of 3 cohorts: subjects with mild hepatic impairment (Child Pugh Class A) will be in Cohort A, subjects with moderate hepatic impairment (Child Pugh Class B) will be in Cohort B, and healthy (control) subjects will be in Cohort C. To qualify for Cohort A or B, the subject must have stable (ie, without any change in disease status for at least 60 days prior to study screening) hepatic impairment conforming to Child-Pugh

classification A or B, respectively (see Table 1 and Table 2), documented by medical history and a physical examination. To qualify for Cohort C, the healthy subject must match a subject with hepatic impairment with regard to age (± 10 years), sex, and BMI ($\pm 20\%$), and as determined by no clinically significant deviation from normal in medical history, physical examination, ECG, and clinical laboratory determinations.

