6.2.2 MELD Score

The MELD score at Screening for each subject (in each of the three cohorts) will be calculated as follows per the OPTN policy, January 2016 (pages 4-5)²:

First the initial MELD score will be calculated:

 $MELD(i) = [0.957 \times log_e(Creatinine)] + [0.378 \times log_e(bilirubin)] + [1.120 \times log_e(INR)] + 0.643$

This value will be rounded to two decimal places and multiplied by 10.

If calculated value for MELD(i) is > 11, the additional MELD calculation will be performed:

 $MELD = MELD(i) + [1.32 \times (137 - Serum Sodium)] - [0.033 \times MELD(i) \times (137 - Serum Sodium)]$

This recalculated MELD value will be rounded to the nearest integer. If $MELD(i) \le 11$ then the recalculated MELD value will equal the initial MELD value.

The following scheduled screening values are used:

- Creatinine in mg/dL
- Bilirubin in mg/dL
- INR
- Sodium in mmol/L

Where the scheduled screening value is missing the first non-missing repeat scheduled value will be used.

The following additional rules will be followed:

- If the Bilirubin, Creatinine, or INR value is <1.0 a value of 1.0 will be used in the calculation.
- If Creatinine>4.0 mg/dL, a value of 4.0 will be used in the calculation
- If Sodium <125 mmol/L, a value of 125 will be used in the calculation.
- If Sodium >137 mmol/L a value of 137 will be used in the calculation.

The maximum MELD score is 40.

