The rules for presenting raw individual values and summary statistics for PK concentration and parameter data are provided in section 6.3.1.

Protein Binding

Blood samples for plasma protein binding for lemborexant will be collected for each subject at 2 time points: 1 hour and 24 hours postdose. Protein binding data will be provided by the vendor to WCT as a percentage; if more than one value is available for either time point, the average of the protein binding values will be used in the calculations. Protein binding results will be presented as fractions and percentages.

Protein binding will be calculated for metabolites without any assessment of PK parameters.

Evaluation of the impact of hepatic impairment on drug exposure:

The effect of hepatic impairment on the PK of lemborexant, the primary PK parameters based on total C_{max} , $AUC_{(0-72h)}$, $AUC_{(0-t)}$, and $AUC_{(0-inf)}$ will be compared between the cohort of healthy normal controls and the cohorts of subjects with mild and moderate hepatic impairment as defined by Child-Pugh classes A or B. A general linear model of logarithmically transformed values with hepatic function class as a fixed effect will be utilized to estimate the geometric mean ratio (and two-sided 90% confidence intervals) of subjects with mild/normal and moderate/normal hepatic function. Similar statistical analyses will be conducted for the PK parameters of the metabolites and unbound lemborexant as secondary endpoints. Protein binding will be calculated for metabolites without any assessment of PK Parameters. Summary statistics will be generated for each of the PK parameters for each Child-Pugh class and healthy controls

Scatter plots of PK parameters (C_{max}, AUC₍₀₋₇₂₎, AUC_(0-t) and AUC_(0-inf)) of lemborexant and its metabolites versus Child-Pugh Score at Screening will be provided. The association between the primary PK parameters and Child-Pugh Score will be evaluated by regression analysis (the PK parameter as a dependent variable and Child-Pugh Score as an independent variable). For subjects in the Healthy cohort the Child-Pugh score will be set to zero in the scatter plots and regression analysis. Similar analyses will be performed for the following measurements at Screening: MELD score, serum albumin, total bilirubin, PT, and creatinine. Additionally, association between the PK parameters and liver transaminase levels at Screening (ALT and AST) will be performed, if deemed necessary.

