	Function (Cohort C) for 1 and 24 hours - PK Analysis Set
14.2.2.12	Scatterplots for Pharmacokinetic Parameters of Lemborexant and
	Metabolites versus Cohort - PK Analysis Set
14.2.2.13	Scatterplots for Pharmacokinetic Parameters Adjusted by Unbound
	Fraction in Plasma for Lemborexant and Metabolites versus Cohort -
	PK Analysis Set
14.2.2.14	Mean and Mean (SD) Lemborexant and Metabolites Concentration-
	Time Profiles after Administration of Lemborexant 10 mg to Subjects
	with Mild Hepatic Impairment (Cohort A), Moderate Hepatic
	Impairment (Cohort B), or Normal Hepatic Function (Cohort C)
	Truncated to 24 hours Postdose on Linear and Semi-Logarithmic
	Scales - PK Analysis Set

Figures renumbered:

Figure	Title
14.2.2.15	Scatterplot and Regression Analysis for Pharmacokinetic Parameters of
	Lemborexant and Metabolites versus Child-Pugh Score at Screening
	PK Analysis Set
14.2.2.16	Scatterplot and Regression Analysis for Pharmacokinetic Parameters of
	Lemborexant and Metabolites versus MELD Score at Screening
	PK Analysis Set
14.2.2.17	Scatterplot and Regression Analysis for Pharmacokinetic Parameters of
	Lemborexant and Metabolites versus Serum Albumin at Screening
	PK Analysis Set
14.2.2.18	Scatterplot and Regression Analysis for Pharmacokinetic Parameters of
	Lemborexant and Metabolites versus Total Bilirubin at Screening
	PK Analysis Set
14.2.2.19	Scatterplot and Regression Analysis for Pharmacokinetic Parameters of
	Lemborexant and Metabolites versus Prothrombin Time at Screening
	PK Analysis Set
14.2.2.20	Scatterplot and Regression Analysis for Pharmacokinetic Parameters of
	Lemborexant and Metabolites versus Creatinine at Screening
	PK Analysis Set
14.2.2.21	Scatterplot and Regression Analysis for Pharmacokinetic Parameters of
	Lemborexant and Metabolites versus ALT at Screening

Template: WCT-TP-ST-008-01 Effective: 14-Feb-13 Page 6 of 9

SCIENTIFICALLY MINDED · MEDICALLY DRIVEN

Eisai, Inc. E2006-A001-104 Post database lock SAP Addendum Version: 1.0 Issue Date: 24-JUL-2018

	PK Analysis Set
14.2.2.22	Scatterplot and Regression Analysis for Pharmacokinetic Parameters of
	Lemborexant and Metabolites versus AST at Screening
	PK Analysis Set

Eisai, Inc. E2006-A001-104 Post database lock SAP Addendum Version: 1.0 Issue Date: 24-JUL-2018

Approval for implementation of Statistical Analysis Plan Post Database Lock Addendum

Title:

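### Healthy subjects enter the Child-Pugh regression at 0, five points below the scale's minimum, so the slope mostly reflects an artificial gap

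*SAP*

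**What the plan says.** SAP section 6.15 plans scatter plots and a regression with the PK parameter as the dependent variable and the Child-Pugh score as a numeric independent variable. For Cohort C it adds: "For subjects in the Healthy cohort the Child-Pugh score will be set to zero in the scatter plots and regression analysis". It does not say whether the PK parameter is log-transformed in this regression.

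Protocol section 9.3.1, Table 1 ("Points Scored for Observed Findings") gives 1, 2 or 3 points to each of five items, and Table 2 begins at 5 (Class A is 5–6, Class B is 7–9). Under protocol section 9.4.3, Cohort C subjects must have "no clinically significant deviation from normal in medical history, physical examination, ECG, and clinical laboratory determinations".

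The regression serves a secondary objective in protocol section 8.2: "To evaluate the relationship between the PK parameters of lemborexant and its metabolites and the Child-Pugh Classification score". Protocol section 7.2.1 would use all 24 subjects and says that the slope "may provide additional indication of any effect (or lack of) on lemborexant PK". Section 7.2.2 says that "the overall conclusions and dosing recommendations will be based on analysis using the Child-Pugh Scores and their relationship with lemborexant PK".

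The post-lock addendum keeps the figure (14.2.2.15, "Lemborexant and Metabolites versus Child-Pugh Score at Screening") and does not change the code. SAP section 9 lists no changes to the protocol's analysis.

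**The concern.** In a class factor the label for healthy subjects is arbitrary. In a numeric regression the distance between codes acts as data. Five items at a minimum of 1 point each total 5, so a subject with five normal findings scores 5 and a score of 0 is impossible. Coding 0 makes the step from healthy to the mildest Class A subject larger than the whole 5-to-9 range among the impaired subjects. Neither document gives a reason.

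The SAP treats its other composite score differently. Section 6.2.2 says the "MELD score at Screening for each subject (in each of the three cohorts) will be calculated as follows", with bilirubin, creatinine and INR floored at 1.0. A healthy subject at those floors gets 0.643 rounded to 0.64, times 10, or 6.4, not 0.

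The slope per point therefore mixes two questions: healthy versus liver disease, and severity among those with liver disease. It can be far too shallow, or it can show a gradient that does not exist among impaired subjects. It is a supporting input to the dosing conclusions, beside the class ratios and the population PK analysis described in protocol section 7.2.

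**Working it through.** **Inputs.** 8 subjects per cohort; Class A scores 5–6, Class B scores 7–9; log-scale SD of AUC(0-inf) 0.391 (protocol 9.7.2, SAP 4); two-sided 90% CIs. Individual scores are not given. Assumed: A = 5,5,5,5,6,6,6,6 and B = 7,7,7,8,8,8,9,9. Ranges come from all 405 possible splits of the two classes. The log scale is also assumed.

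**The plan's own figure.** 1.645 × 0.391 × √(1/8 + 1/8) = 0.322, as stated. The documents give no figure for the regression.

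**Weight of the healthy-versus-impaired contrast.** With healthy subjects coded h, the least-squares slope is

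b = w × (mean log difference, impaired − healthy)/(6.6875 − h) + (1 − w) × (slope within A and B), where w = between-group sum of squares / Sxx.

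- Impaired mean: (44 + 63)/16 = 6.6875.
- Within-impaired sum of squares: 745 − 107²/16 = 29.44.
- Between-group sum of squares: (8 × 16/24) × (6.6875 − h)² = 238.52 at h = 0 and 15.19 at h = 5.
- w at code 0: 238.52/267.96 = 89% (80–98% over the 405 layouts). w at code 5: 15.19/44.63 = 34%.

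The eight healthy points' own share of Sxx is a different quantity: 59% at code 0 (54–66%) and 23% at code 5 (14–50%).

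**Exposure linear in the score from 5, slope β.** At code 0 the between-group slope is β × 1.6875/6.6875 = 0.252β. Then b = 0.890 × 0.252β + 0.110 × β = 0.33β (0.23–0.43β over the layouts). In 40,000 simulated trials the zero-coded 90% CI covered the true slope about 15% of the time at β = 0.1 and about 0% at β = 0.2. Code 5 and the A-and-B-only fit both covered it 90% of the time.

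**Other patterns** (assumed geometric mean ratios to healthy; slope of log exposure per point):

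| Mild / moderate | Code 0 | Code 5 | A and B only |
|---|---|---|---|
| 1.0 / 2.0 | 0.071 | 0.217 | 0.224 |
| 1.25 / 1.5 | 0.048 | 0.102 | 0.059 |
| 1.5 / 2.0 | 0.083 | 0.172 | 0.093 |
| 1.5 / 1.5 | 0.054 | 0.082 | 0.000 |

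Example, last row at code 0: 0.890 × ln(1.5)/6.6875 = 0.054. In that row the 90% CI excludes zero in 70% of trials at code 0 (66–75% over six layouts), 34% at code 5 and 10% for A and B only.

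**No effect of any kind.** All three fits exclude zero about 10% of the time, as they should.

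**Precision.** The slope SE is 0.391/√Sxx: 0.024 at code 0, 0.391/√44.63 = 0.059 at code 5, and 0.391/√29.44 = 0.072 for A and B only.

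**Indicator model.** Adding a healthy/impaired indicator to the 24-subject regression reproduces the A-and-B-only slope under either code (0.093 for 1.5/2.0), with 21 rather than 14 residual degrees of freedom.

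**The case against.** The strongest objection is to recoding as a remedy. Taking the A-and-B-only slope as the reference, code 0 is closer than code 5 in three of the four tabulated patterns. Code 5 also puts healthy people level with stable Class A patients who score 5, which is itself an assumption. This stands: recoding alone does not cure the problem.

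Second, using all 24 subjects was meant to help detect a relationship, and that ability falls. The 90% CI excludes zero at code 0, at code 5 and in A and B only in about 62%, 50% and 20% of simulated trials for pattern 1.25/1.5, and 96%, 85% and 33% for 1.5/2.0. The loss is real. But much of the detection at code 0 is the healthy-versus-impaired contrast, which the primary ratios already estimate.

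Third, the shrinkage to one third and the poor coverage hold only if exposure is linear from 5. That is so, and the direction of the distortion is not known in advance. The weight of 80–98% does not depend on the exposure pattern.

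Fourth, no decision threshold is set on the slope, the test under no effect is valid, and protocol section 7.2.1 speaks of apparent clearance whereas the SAP regresses the primary parameters. These points limit the seriousness. On the log scale CL/F = Dose/AUC(0-inf) only reverses the sign of the AUC(0-inf) slope, though this does not extend to Cmax.

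**Conclusion.** The concern holds. The code of 0 is impossible on the protocol's own scale, is not justified anywhere, and sets at least 80% of the slope's weight under every possible layout of scores. Depending on the exposure pattern, the result can be a slope about one third of the true one, or an apparent gradient where impaired subjects show none. The slope and simulation figures rest on a log scale, an SD of 0.391 and an assumed spread of scores.

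The mild/normal and moderate/normal ratios use class as a factor and are unaffected, as are the regressions on MELD, albumin, bilirubin, PT and creatinine. This should be fixed because it concerns a named secondary objective that feeds the dosing conclusions. It does not threaten the primary analysis.

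**What to change.** In SAP section 6.15:

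1. Replace the zero code by scoring Cohort C on Table 1 (5 when all findings are normal), in both the plots and the regression.
2. Report beside it the regression in Cohorts A and B only (N = 16), and read the per-point slope from that fit. Equivalently for the slope, add a healthy/impaired indicator to the 24-subject model, which keeps more residual degrees of freedom.
3. State that the PK parameter is log-transformed.

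The statistical price is the wider slope interval and lower detection rate set out above; the report should say so. The practical cost is one SAP sentence, one added model and a rerun of the Child-Pugh figure (14.2.2.15 in the addendum). The screening laboratory tests and physical examination are already scheduled for every subject, so no new data are needed. Because the addendum postdates database lock, the change has to be disclosed as made after lock.

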6.16 Pharmacogenomic Analysis

Not Applicable.

6.17 Safety Analyses

The safety analyses will be presented by cohort for the Safety Analysis Set.

6.17.1 Adverse Events

A treatment-emergent adverse event (TEAE) is defined as an AE that emerges during treatment, having been absent at pretreatment (Baseline) or

- Reemerges during treatment, having been present at pretreatment (Baseline) but stopped before treatment, or
- Worsens in severity during treatment relative to the pretreatment state, when the AE is continuous.

The following tables will be presented for AEs:

- Overall incidence by cohort in the number of TEAEs, SAEs and events associated with special situations, AEs related to study treatment, SAEs that are related to study treatment, AEs leading to discontinuation and Potential Cataplexy AEs (as defined in Section 6.2.8).
- TEAEs by system organ class and preferred term incidence.
- TEAEs by system organ class, preferred term and maximum severity incidence
- Treatment-related TEAEs by system organ class and preferred term -.
- SAEs and deaths by system organ class and preferred term incidence overall and for those related to treatment.

• Treatment-emergent, non-serious AEs by system organ class and preferred term – incidence overall and for those related to treatment.

A subject will only be counted once within a specific system organ class and preferred term, even if the subject experienced more than one TEAE within that specific system organ class and preferred term.

Listings of adverse events will be provided in the following categories:

- TEAEs
- Non treatment-emergent AEs
- Deaths
- Serious TEAEs and events associated with special situations
- AEs leading to discontinuation
- Potential Cataplexy AEs

If an AE has missing relationship it is assumed to be related to the study drug for the purpose of summarizing the data. For an AE with missing severity the severity will be reported as "missing" if the subject has not reported another AE within the same level of summarization (i.e. system organ class or preferred term). If the subject has reported more than one AE within the same level then the worst severity will be used in the tabulation.

For Potential Cataplexy AEs data from the supplemental information questionnaire will be listed.

